4.0 Study Intervention(s)/Interaction(s)

4.1 Description: Researchers will interact with study participants during Phase I and Phase II (Table 1). In Phase I, researchers will enroll 20 PWMC and their care partners to participate in a dyadic interview session. The dyadic interviews will occur via the HIPAA-compliant video conferencing platform, Zoom. The interviews will begin with questions

SOCIAL PROTOCOL (HRP-580)**PROTOCOL TITLE: A Mobile Informatics Solution to Aid in Memory****VERSION DATE: 7/1/2022**

about the participants' technology use prior to and during the COVID-19 pandemic then participants will watch a brief instructional video followed by a question and answer session on the smartwatch technology, a verbally administered survey, and end with a semi-structured discussion about the SR. In Phase II, researchers will enroll 100 PWMC and their care partners to participate in initial, 3-month, and 6-month surveys. Half of the dyads will be randomly assigned to receive the smartwatch technology for a 6-month period and the other half will be randomly assigned to the usual care control group. 20 PWMC and their care partners who receive the smartwatch technology will be asked to participate in a semi-structured interview in the month following their 3 or 6-month survey.

Table 1. Phase I and II Schedule for AME Developers and UMN-Affiliate Researchers

	Months 1-6	Months 7-12	Months 13-24	Months 25-36
Project Management: Weekly Web Conference and Annual In-Person Meetings	•	•	•	•
● Recruit and train RA ● Build Smartwatch Reminder ● Data management and entry protocols	•	○	○	○
Phase I (Months 1-12)				
● Enroll 20 PWMC and their care partners	•	○		
● Complete dyadic interviews	•	○		
● Analyze Phase I qual/quan data ● Refine Smartwatch Reminder content and protocol for Phase II	○	•		
Phase II (Months 12-36)				
● Enroll 100 PWMC and their care partners			•	○
● Complete initial, 3-month, 6-month, and embedded qual data collection			•	•
● Analyze qual/quan data			○	•
● Disseminate Phase II findings			○	•

NOTE: RA = research assistant; PWMC = persons with memory concerns; qual = qualitative; quan = quantitative; • = primary focus; ○ = secondary focus

5.0 Procedures Involved

SOCIAL PROTOCOL (HRP-580)

[figure not shown]
PROTOCOL TITLE: A Mobile Informatics Solution to Aid in Memory

VERSION DATE: 7/1/2022

5.1 Study Design: The proposed study will enable us to investigate the utility of the Smartwatch Reminder for individuals with varying degrees of memory concern. We will evaluate the immediate utility of the Smartwatch for persons with memory concern, and determine the extent to which participants practice using the system in the three months after it is introduced. By including participants with mild-to-moderate cognitive impairment we will also ascertain the feasibility of starting to use the Smartwatch system at a time when participants may immediately benefit from the cues and information provided by the system. Through interview questions, we will probe PWMC and their care partners to understand if using the Smartwatch in the early stages of cognitive decline is a valuable experience and if they would consider using the Smartwatch as the PWMC experiences cognitive decline.

AME has assembled an interdisciplinary team with the necessary skills to achieve the objectives of the project and effectively carry out the study design (Figure 1). [name] at AME is an experienced Primary Investigator with decades of project management and electronics engineering experience. AME's [name] has worked on multiple smartphone and smartwatch projects and has published papers on them. [name] and [name] at AME are the Technical Managers on the study. AME has also partnered with [name], [name] and [name] as engineers.

Figure 1. Structure of Industry and Academic Study Collaborators

The Principal Investigator in Phase I, [name], PhD, at the University of Minnesota has an established track-record of conducting research on PWMC and their care partners. He has built on his well-established research foci to apply novel technologies that assist family and professional caregivers of persons with dementia. The Principal Investigator in Phase II, [name], at the University of Minnesota has acted as a consultant to faculty

SOCIAL PROTOCOL (HRP-580)

PROTOCOL TITLE: A Mobile Informatics Solution to Aid in Memory

VERSION DATE: 7/1/2022

and investigative teams in the areas of project development, research design, and grant development. In addition, he is an expert in qualitative research methods, transition-related stress, computer-mediated communication and computer-mediated social support. Collaborating Co-Investigators on this project include [name] (PhD and Assistant Professor of Psychology at Emmanuel College), [name] (PhD and Postdoctoral Research Fellow in the University of Michigan Institute for Social Research), and [name] (PhD and Assistant Professor in the Brown School of Public Health and researcher at the Center of Innovation in Long-Term Services and Supports at the Providence VA Medical Center). The Co-Is have collaborated extensively with [name] and each other on multiple evaluations of interventions and services for PWMC, including innovative technological interventions in dementia care projects. This includes evaluating a remote activity monitoring program that installed sensors in the home of a PWMC. Each investigator also has independent expertise in qualitative, quantitative, and mixed-methods research and participation in multiple randomized trials. [name] is a psychologist with expertise in social support and adult development, and a focus on mixed methods. [name] is a health geographer and environmental gerontologist whose methodological expertise include global positioning systems tracking, in-person and virtual geospatial audits, interviews, surveys, and cognitive and physical testing. [name] is a health services researcher focused on understanding the cost and value of care provided to individuals with PWMC. His prior work includes conducting a cost-effectiveness study alongside a randomized trial evaluating a dementia caregiver support program and evaluating the effect of cognitive decline on time spent providing informal caregiver. Our team of collaborators is well-positioned to conduct an evaluation of the Smartwatch Reminder (SR).

5.2 Study Procedures:

Phase I Feasibility Pilot Study

Overview. The objective of Phase I is to make an initial, limited assessment of the value of the Smartwatch Reminder (SR) for PWMC and their care partners.

Phase I Sample Size. The academic team will purposively sample 20 dyads (PWMC and their care partners) of varying kin relationships (adult child vs. spouse), gender, and race/ethnicity to participate in Phase I feasibility testing.

Phase I Procedure. A parallel-convergent mixed methods design (QUAN+QUAL) will be used to generate qualitative and quantitative data on the feasibility and utility of the SR system.

1. **Initial Contact:** During initial contacts with potential participants, the RA will explain the study procedures and invite care partners to participate in the study. Care partners will have the opportunity to ask questions about the study procedures.
2. **Enrollment:** If the care partner agrees to participate, the RA will screen the participant and schedule the dyad for a dyadic interview session (see Section 9, "Study

SOCIAL PROTOCOL (HRP-580)

PROTOCOL TITLE: A Mobile Informatics Solution to Aid in Memory

VERSION DATE: 7/1/2022

Population"). An email will be sent to the participants containing an instructional pamphlet to read over before the interview.

3. **Consent:** The RA will first ensure that the dyad is able to use the video conferencing platform and troubleshoot any issues that may have occurred. The RA will then obtain informed consent from the care provider and PWMC (see Section 21, "Consent Process").
4. **Dyadic Interview Sessions:** The RA will digitally record each session. Audio recordings will be transcribed by a professional transcriptionist. The interview will begin with the context of care questions (see Appendix). Participants will then be asked questions on technology use prior to and during the COVID-19 pandemic. The RA will then play a video on how to use the SR system to the PWMC and their care partner. Next, participants will ask the RA questions they have about how the technology works (e.g., navigating the smartphone app; entering new profiles, photos, and information; using the smartwatch to identify the caregiver and other persons nearby).

Immediately after the SR tutorial, participants will be asked to complete a brief survey including the SR checklist to evaluate their perceptions of the technology. Questions will be asked verbally during the interview session. The SR checklist includes Likert items designed to measure both the PWMC and care partners' perceptions of the performance of SR in terms of ease of use, clarity, and quality of information provided.

The RA will then ask the participants semi-structured questions to elicit open-ended data on the feasibility and utility of SR (see Appendix). The interview questions include prompts about technology more generally to elicit feedback about opportunities and barriers for technology to assist care partners and PWMC in navigating everyday life. This will provide a more comprehensive perspective regarding the feasibility and use of the SR system. Participants will provide in-depth information on the reasons why PWMC and care partners felt the SR will or will not be easy to use, and will point out barriers or facilitators to use that will be critical to address when refining SR prior to Phase II.

Phase I Data Collection.

18-item system review checklist. This will be completed verbally by care partners and PWMCs during the dyadic interviews. The checklist includes Likert items designed to measure both the PWMC and care partners' perceptions of the performance of SR in terms of ease of use, clarity, and quality of information provided.

Context of care. Questions will be completed verbally during the dyadic interviews. Care partners and PWMCs can complete the context of care variables. It includes items on geographic location, time since diagnosis, type of dementia diagnosis, Medicaid status, living arrangement of the PWMC, and demographics of the PWMC and the care partner.

Semi-structured questions. The RA will conduct dyadic interviews with Phase I participants to elicit open-ended data on the feasibility and utility of SR. Questions will also elicit feedback on how participants' technology use has changed due to the COVID-19

pandemic. The semi-structured questions will provide in-depth information on the reasons why PWMC and care partners felt the SR was or was not easy to use, and will point out barriers or facilitators to use that will be critical to address when refining SR prior to Phase II (33).

Phase II. Evaluate the Smartwatch Reminder Efficacy

Overview of Phase II. The primary goal of the SR is to facilitate social interaction for PWMC by providing facial recognition of family, friends, and other key people. In this Phase II study, the SR will be evaluated to determine whether it provides positive benefits for PWMC's social interactions and well-being.

Phase II Sample Size. 100 dyads (PWMCs and their care partners) will be enrolled. Half of the PWMCs will be randomly assigned to the intervention group (i.e., use of SR) and half to the attention control group. The intervention group will receive the SR.

Procedure. An embedded experimental mixed methods design ([QUAN+qual]→[QUAN+qual])(12) will be utilized to combine the collection and analysis of qualitative data within a traditional randomized controlled trial design(12). This will assist the project team in examining the process of the SR's implementation during the evaluation to determine whether or not and why the SR worked for PWMCs and their care partners(12, 34, 35).

Pilot Testing. Prior to initiating full recruitment, we will pilot test the Smartwatch System technology among 1-2 dyads. This will ensure that any possible bugs in the Smartwatch System are worked out before many more dyads are enrolled and given the technology. If no or very minimal problems are found, the 1-2 dyads would remain in the study and be included in the total of 100 dyads recruited. If many problems are found, the 1-2 dyads would remain in the study, but their data would not be used, so 100 more dyads would still need to be recruited.

1. **Initial Contact:** During initial contacts with potential participants, the RA (or, if needed, Drs. [name], [name] and [name] or the research coordinators) will explain the study procedures and invite care partners to participate in the study. Care partners will have the opportunity to ask questions about the study procedures.
2. **Enrollment:** If the care partner agrees to participate, the RA will schedule a brief screening and enrollment procedure using the inclusion criteria (see Section 9, "Study Population"). The RA will obtain informed consent/assent from the care partner and PWMC (see Section 21, "Consent Process").
3. **Baseline survey:** Following enrollment, a baseline survey will be administered to both the CP and PWMC (either online in Qualtrics or via mail, if preferred) within 2 weeks of enrollment (see Appendix). The RA will administer this prior to exposure to the intervention/attention control.
4. **Randomization:** Following completion of the baseline survey, PWMC and their care partners will be randomly assigned to the SR treatment condition that receives full access

SOCIAL PROTOCOL (HRP-580)

PROTOCOL TITLE: A Mobile Informatics Solution to Aid in Memory

VERSION DATE: 7/1/2022

to the SR along with the training procedures or an attention control group. Randomization (participant is assigned to either the treatment or control condition) will be completed via an a priori list generated from <http://randomizer.org> by [name]. For those in the SR treatment group, the research coordinator will schedule a time to introduce the SR to the PWMC and the care partner via Zoom or telephone.

To ensure blinding is maintained, the RA will not have access to the password-protected database containing participants' group assignment, and will not review survey data completion (which would un-blind the RA since all of the treatment participant follow-up surveys will contain the system review and all control participant follow-up surveys will not). Additionally, opaque, sealed envelopes will be created for the research coordinator to reveal which group each participant was randomized into. The outside of each envelope will be labeled with a dyad's ID and the inside will contain their group assignment, which will ensure integrity of the randomization order since no one will be able to change the order once the envelopes are created.

5. **3-month survey or contact call:** A survey will be administered (either online in Qualtrics or via mail, if preferred) by the RA to all participating care partners and PWMC 3 months following enrollment. A brief disposition survey will be administered before the 3- and 6-month follow-up surveys to determine if the PWMC has moved or passed away. A system review of the SR will be assessed via a checklist and open-ended questions (see Appendix) and will be sent only to dyads in the intervention group in their follow-up survey (the RA will remain blinded because they will email participants personalized links to the survey which do not indicate whether the participant is receiving the SR system review or not in their follow-up survey). The attention control group will receive a 3-month contact call from the research coordinator. Based on our prior experience, PWMC and care partners in an attention control group will often seek information and psychosocial support during these calls. We will provide free information resources (e.g., brochures or websites of the Alzheimer's Association). See section 10.2 about re-assessing each PWMC's capacity to consent at each time point.
6. **6-month survey or contact call:** A survey will be administered (either online in Qualtrics or via mail, if preferred) by the RA to all participating care partners and PWMC 6 months following enrollment. A brief disposition survey will be administered before the 3- and 6-month follow-up surveys to determine if the PWMC has moved or passed away. Additionally, a system review of the SR will be administered by the RA to participating care partners and PWMC in the intervention group 6 months following enrollment (while remaining blinded). The attention control group will receive a 6-month contact call from the research coordinator.
7. **Data tracking for 6 months:** Detailed data on frequency and duration of use by PWMC and their care partners will be tracked directly by the SR, allowing for an analysis of exact utilization and practicality (i.e., how long and often PWMC and their care partners actually use the technology). This data will be shared with us securely via Box by AME.
8. **Semi-structured interview:** 20 semi-structured interviews will take place up to one month after completion of the final 6-month follow-up survey with intervention group participants only. Due to a change in study funding and timeline, as of 9/1/23, to meet the

SOCIAL PROTOCOL (HRP-580)

PROTOCOL TITLE: A Mobile Informatics Solution to Aid in Memory

VERSION DATE: 7/1/2022

20 semi-structured interviews, some semi-structured interviews will now take place following the 3-month follow up survey with intervention participants. Dyads will complete only one interview at 3 or 6 months, not at each time point.

Note: Baseline and follow-up surveys and interviews will be in a format that is convenient to care partners and PWMCs: through online or mail formats, whichever is desired by the individual. Each baseline survey is anticipated to take no more than 45 minutes to complete with follow-up surveys expected to take approximately 20-30 minutes to complete. If the PWMC has passed away or moved into a long-term care facility as determined by the brief disposition survey at 3- or 6-months, the PWMC would not be administered any additional surveys and the care partner would receive shortened follow-up surveys if they agree to continue, depending on the person with memory concern's scenario (bereavement or transition to a long term care/assisted living facility).

The RA will complete disposition calls or emails ± 7 days prior to a scheduled follow-up survey. The RA will contact care partners within 1 week of a missed survey to resend, and update participants' contact information as needed throughout the project. RA will follow up with CG and PWMC via email reminders at 1, 2 and 3 weeks past the date a survey was sent if it is still incomplete. Additionally, at 3 weeks RA/RC will try to contact dyad via phone. If no response, participants will be considered lost to follow up (LTFU) for that time point.

Note: If LTFU occurs at baseline, the dyad will be withdrawn from study as they were not randomized.

An annual project newsletter will be sent to all participants to provide updates on study progress as well as provide seasonal caregiving tips. Finally, in order to provide additional rapport and incentive to participate in the attention control group, all PWMC and care partner dyads in the proposed project will be provided with up to a \$100 participation incentive following completion of their 6-month survey (see more information in Payment section 12.5). Those in the treatment group who are selected for and complete a semi-structured interview will receive an additional \$50 participation incentive.

Phase II Data Collection.

The RA will administer the baseline and follow-up surveys at 3- and 6-months, and will be blinded to randomization. Completion of these follow-ups may occur outside of the timeframe for initial contact based on participant scheduling needs.

Baseline, 3-Month and 6-Month Survey. The RA will administer all surveys (see Appendix). The surveys are designed to collect information from both PWMC and care partners. The selected measures have strong psychometric properties, sensitivity to change, and clinical relevance in the evaluation of health technology such as SR. Our past experience in distributing surveys of similar length indicate that they take PWMC and their care partners approximately 20-45 minutes to complete. Mean and sum scores will be calculated for all scales.

SOCIAL PROTOCOL (HRP-580)

PROTOCOL TITLE: A Mobile Informatics Solution to Aid in Memory

VERSION DATE: 7/1/2022

- Context of care (baseline only). Care partners will complete context of care variables include geographic location, time since diagnosis, type of dementia diagnosis, Medicaid status, living arrangement of the PWMC, and demographics of the PWMC and the care partner.
- Dementia severity. Care partners will complete validated measures of dementia severity including the PWMC's dependence on assistance with 6 activity of daily living tasks and dependence on assistance with 6 instrumental activity of daily living tasks(16-18, 50-52). An 8-item scale will assess the intensity of PWMCs' memory losses, communication deficits, and recognition failures at each time point (memory impairment)(19, 20). From the Dementia Severity Rating Scale, we are using one item about the PWMC's recognition of others (53). Additionally, during screening, the PWMC will complete the Telephone Interview for Cognitive Status (TICS-40) developed from the Aging, Demographics, and Memory Study), which will assess their level of dementia severity at the beginning of the study (50).
- Social interaction. Questionnaires will be administered to care partners to determine the frequency and quality of PWMCs' interaction in six different areas: in-person visits; telephone/video calls; traditional mail correspondence, text messaging, or email; and social media. Per the recommendations of prior research on informal long-term care, a prior week estimate will be completed that includes frequency and duration of each activity(22). A 7-day time-window was chosen as it is less prone to recall error. In addition to frequency data, satisfaction with the quality of interaction will be assessed on a simple 5-point scale, similar to prior reliable measures utilized in Alzheimer's disease and related dementias care partner intervention studies(23).
- Pleasant Events/Social Engagement. Care partners will complete the Pleasant Events Schedule-AD (PES-AD) Short Version (24, 25) for PWMCs. The PES-AD Short Version includes 20 items of events and activities for PWMCs. As originally constructed, the items of the PES-AD were within the capacity of individuals suffering from the earlier/milder stages of dementia, and thus were appropriate for inclusion in this Phase II project(24, 25). Items are rated according to their frequency during the past month and how much the PWMC enjoys the activity. An overall summary score assessing frequency of engagement in enjoyable activities is generated by multiplying each frequency and enjoyment item with each other and summing the resulting responses. The PES-AD has demonstrated excellent reliability and validity(24, 25).
- Global Health. The PWMCs' overall health and quality of life are being measured using the PROMIS Scale v1.2 – Global Health (26). This assesses various aspects of health and life, such as ratings of mood, satisfaction with social activities/relationships, average pain, etc. through a series of 10 questions asked of the PWMC.
- Mobile Device Proficiency and social media use. The Mobile Device Proficiency Questionnaire (MDPQ-16; short form) is a 16-item scale used to measure how proficient the CP and PWMC are using various new technologies, such as tablets and their different features (27). The CPs' social media usage is also being measured using 3 questions developed by the research team.

SOCIAL PROTOCOL (HRP-580)

PROTOCOL TITLE: A Mobile Informatics Solution to Aid in Memory

VERSION DATE: 7/1/2022

- Social Support/Loneliness. Socioemotional support will be measured on a five-item scale to assess the affective assistance provided to the care partners by relatives or friends at each time point(19, 20). The Lubben Social Network Scale-6 (LSNS-6) is a six-item scale that assesses social isolation among the CP and PWMC (55). Loneliness will be measured with the 3-item Short Scale for Measuring Loneliness in Large Surveys(28).
- Care partner well-being. The 11-item Eriksonian Psychosocial Stage Inventory - Identity scale(29) will be administered to assess changes in identity coherence. The 10-item Center for Epidemiological Studies-Depression scale will be used to measure care partner depressive symptoms(30, 31).
- Relationship closeness. A 6-item measure of Relationship Closeness (32) will be used to evaluate the quality of the relationship between the PWMC and their care partner. This 6-item measure is part of the Stress Process Model for Residential Care (SPM-RC), developed by Whitlatch and colleagues and based on the Stress Process Model (SPM) for dementia caregiving. The measure assesses caregiver agreement with statements about their relationship with their relative using a 4-point Likert scale (1=strongly disagree, 4=strongly agree). Higher scores indicate a closer relationship (range 6-24).
- Community engagement. A 15-item survey developed specifically for the project will evaluate the PWMC's typical social interactions and destinations accessed outside of the home. The survey evaluates average frequency of leaving the home; socializing in-person with family and friends; and destinations accessed including senior centers, gyms and recreational facilities, educational classes, libraries, faith services, club meetings, coffee shops/cafes, and parks. Following the 15-item survey, an open-ended question to be applied post-baseline asks in which situations the SR system was and was not useful, and why.
- Caregiving Burden. A short version of the Burden Scale for Family Caregivers (BSFC-s) is a valid measure of subjective burden among family caregivers and is measured using 10-items on a 4-point scale (54).

Phase II will also feature 20 semi-structured interviews with purposively sampled dyads who are randomly assigned to receive SR. These interviews will take place up to one month after completion of the final 6-month follow-up survey. As of 8/31/2023 due to funding and timeline changes, interviews may also take place up to one month after completion of the 3-month follow-up survey. Dyads will only complete an interview at one time point (not both). It was determined that interviews at 3 months will be as rich in data as the 6 month surveys. A sequential mixed methods sampling approach will be utilized(36) where the results of the first methodological strand will inform the selection of participants in this second methodological strand. Specifically, the academic collaborators (led by [name]) will purposively select 10 dyads who report average system review checklist scores between 4 and 5 (i.e., SR met their needs) and 10 dyads who indicate average system review checklist scores of 3 and below (i.e., neutral and below regarding SR meeting their needs). A stratified purposive sampling approach will be applied: the academic collaborators will identify family care partners of different kin

SOCIAL PROTOCOL (HRP-580)

PROTOCOL TITLE: A Mobile Informatics Solution to Aid in Memory

VERSION DATE: 7/1/2022

relationship (care partner is spouse vs. adult child), PWMC with varying dementia severity (middle versus late stage dementia symptomatology), caregiver gender, and racial or ethnic background of caregivers to participate.

The open-ended responses of the semi-structured interviews will provide in-depth information on the reasons why dyads felt SR did or did not enhance their interactions with each other and their friends and family. The research assistant will schedule and conduct the semi-structured interviews and will digitally record each one with permission. If permission to record the interview is not granted, relevant field notes will be taken during and immediately following the interview. Audio recordings will be transcribed by a professional transcriptionist into a Microsoft Word file which will then be uploaded to NVivo (37) for subsequent analysis. This mixed methods design will allow the research team to link the efficacy results of the study to the thematic categories developed from the semi-structured interviews.

5.3 Follow-Up: N/A: The study team will not conduct long-term follow up with study participants.

5.4 Individually Identifiable Health Information: N/A: The research team will not access any medical records or other sources of private information about participants, apart from the information provided directly by participants in surveys, interviews, or direct communication with research team members.

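### Device performance decides whether the 1–2 pilot dyads' data are used, and the plan does not say how those dyads are assigned

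*Combined protocol and SAP*

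**What the plan says.** Section 5.2, Phase II, Pilot Testing: before full recruitment, "we will pilot test the Smartwatch System technology among 1-2 dyads", so that faults "are worked out before many more dyads are enrolled and given the technology". Two outcomes are then provided for. In the first, "If no or very minimal problems are found, the 1-2 dyads would remain in the study and be included in the total of 100". In the second, "If many problems are found, the 1-2 dyads would remain in the study, but their data would not be used", and a further 100 dyads are recruited.

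The rest of Section 5.2 describes the 100 as a randomised set. Under Phase II Sample Size, "Half of the PWMCs will be randomly assigned to the intervention group (i.e., use of SR) and half to the attention control group". Step 4 (Randomization) says "Following completion of the baseline survey, PWMC and their care partners will be randomly assigned to the SR treatment condition that receives full access", or to attention control. Assignment "will be completed via an a priori list generated from" an online tool and is revealed from sealed envelopes. Step 4 neither includes nor exempts the pilot dyads.

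Sections 3.1 and 17.1 take randomised group as the main independent variable. Neither section says how retained pilot dyads are to be handled.

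**The concern.** Membership of an efficacy analysis set should be fixed by assignment, not by what happened once treatment began. Here the same 1–2 dyads are in or out depending on how well the device worked for them. The two levels of trouble are not defined, cases in between are not covered, and no decision-maker or time point is named. The decision is therefore discretionary and can be taken with knowledge of how the dyads fared.

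At stake is mainly the integrity of the randomised set: whether every analysed dyad was randomised, and whether every randomised dyad is analysed. A secondary worry is a small tilt towards the device. Its hoped-for benefit works through a functioning watch, so dyads kept because the watch worked may do somewhat better than those dropped because it did not. The link is most direct for the Section 17.1 analyses of how variation in device use relates to outcome, because faults can themselves reduce use.

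**Working it through.** **Do pilot dyads receive the device?** The plan does not say so outright, but a control dyad cannot test a watch. Under independent 1:1 assignment (an assumption), a one-dyad pilot would fail to test the device with probability 0.5, and a two-dyad pilot with probability 0.5 × 0.5 = 0.25. Receipt of the device is therefore strongly implied. How the dyads come to be assigned to it is left open.

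**Both readings against both branches.**

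| | Few or no problems: data kept | Many problems: data not used |
|---|---|---|
| Not from the list | Non-randomised dyads enter the comparison | No harm: the 100 are all new dyads |
| Randomised to the device | No harm: randomised dyads are analysed | Post-randomisation exclusion, device arm only |

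Each reading has one branch that damages the comparison.

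**Size of a possible bias.** From the documents: m = 1 or 2 pilot dyads; 100 dyads split equally, so 50 per arm; alpha 0.05 (Section 17.2). Assumed, because the documents give no figure: the pilot dyads differ from the rest of their arm by b = 0.5, 1 or 2 SD of the quantity compared.

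- Shift in the arm difference = m × b / 50.
- Standard error at 50 per arm = √(2/50) = 0.20 SD.
- δ = shift / 0.20.
- Two-sided type I error = 1 − Φ(1.96 − δ) + Φ(−1.96 − δ), a normal approximation.

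| m | b (SD) | shift (SD) | δ (SE) | type I error |
|---|---|---|---|---|
| 1 | 0.5 | 0.01 | 0.05 | 0.0503 |
| 1 | 1 | 0.02 | 0.10 | 0.0511 |
| 1 | 2 | 0.04 | 0.20 | 0.0546 |
| 2 | 0.5 | 0.02 | 0.10 | 0.0511 |
| 2 | 1 | 0.04 | 0.20 | 0.0546 |
| 2 | 2 | 0.08 | 0.40 | 0.0685 |

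The table models retained dyads who do better than the rest. Dropping randomised dyads who do worse gives nearly the same shift: with 50 others in the arm, two dyads at 2 SD give 2 × 2/52 = 0.077 SD.

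**Cost of leaving the dyads out, by the plan's own method.** Section 17.2 states N = 97 for a multiple regression with 6 predictors, effect size 0.15, alpha 0.05 and power 0.80. Taking 0.15 as f², with 6 and N − 7 degrees of freedom and noncentrality 0.15 × N, power is 0.798 at N = 97 and 0.804 at N = 98. The plan's figure therefore reproduces to within one dyad. By the same formula:

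- 100 dyads: 0.813.
- 99 or 98 dyads (pilot dyads left out and not replaced): 0.809 or 0.804.
- After 3% attrition: 100 × 0.97 = 97 gives 0.798; 99 × 0.97 ≈ 96 gives 0.793; 98 × 0.97 ≈ 95 gives 0.788.

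**The case against.** The strongest defence is that the pilot is a staggered launch. No exception to step 4 is written, retained dyads belong to a total described as randomised, and the first dyads drawn to the device could serve as the test. A reader might infer that pilot dyads are handed the watch outside the list, but the text does not establish that. This part of the defence stands, and the lack of any statement on assignment is itself part of the gap.

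Second, a reader might call the retained data selected on results. The criterion is technical trouble, not any endpoint in Section 3.1 or 17.1. Setting aside data from a device whose faults are about to be repaired has a rationale, and dyads kept after a clean pilot would presumably use much the same device as later ones. This also stands: the selection is on device performance, and its link to outcome is plausible but not shown.

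Third, the direction of bias is not guaranteed. Few faults do not imply better loneliness or burden scores, and hand-picked dyads could have a better or worse prognosis.

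Fourth, at most 2 of 100 dyads are involved. The effect is slight over most of the assumed range.

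What the defence does not answer is the rule itself. Under either reading, one branch lets device performance decide who is analysed, and nothing elsewhere in the plan corrects for it.

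**Conclusion.** The point holds as a flaw in the rule for who is analysed. Use of the pilot dyads' data is tied to undefined levels of device trouble, and their assignment is not stated. The result is either non-randomised dyads in the efficacy set or a post-randomisation exclusion possible only in the device arm.

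The numerical consequence is small: a shift of 0.01–0.08 SD (0.05–0.40 SE) and two-sided type I error of about 0.050–0.069. The upper end needs two dyads who are both 2 SD better than the rest. These figures rest on the assumed 0.5–2 SD, on 50 dyads per arm and on a normal approximation. Bias towards the device is the expected direction, not a certain one; the documents do not support saying that it could only go that way. The case for change rests on the integrity of the randomised set and the negligible cost of repair, more than on the size of the bias.

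**What to change.** State in Section 5.2 how the pilot dyads are, or were, assigned, and replace the two performance-dependent sentences with a rule based on assignment:

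- Pilot dyads not assigned from the sealed-envelope list are excluded from all Phase II efficacy analyses whatever the pilot shows. Their data may be used descriptively. The 100 counts only dyads assigned from the list.
- Pilot dyads assigned from the list are kept in the efficacy analysis whatever the pilot shows.

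Excluding pilot dyads in every case would not do, because if they were randomised it would itself remove randomised participants.

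The revision history dates the pilot to revision 9 (5/25/2022), and the current version is 19 (8/31/2023), so the pilot may be over. In that case, record how the dyads were assigned and adopt the same text as an analysis-set rule before analysis begins.

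The cost is a short change of text and at most 1–2 fewer analysed dyads, or 1–2 replacements. Without replacement, power by the plan's method falls from 0.813 to no lower than 0.804 before attrition, and from 0.798 to no lower than 0.788 after 3% attrition. With replacement it does not change.
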